For Canada (and any other country where applicable or where requested by Regulatory Authorities), the primary efficacy variable is the ASAS40 response at Week 12. The secondary efficacy variables are ASAS40 response at Week 52, ASDAS-MI at Week 52, change from Baseline in BASFI at Weeks 12 and 52, change from Baseline in BASDAI at Weeks 12 and 52, change from Baseline in SI joint SPARCC score at Week 12, the number of subjects without relevant changes to background medication, change from Baseline in ASQoL at Week 52, change from Baseline in nocturnal spinal pain (NRS) at Week 52, and the number of subjects with AU or new AU flares through Week 52.

Other efficacy variables are listed in [Section 4.1.3](#).

---

Pharmacokinetic, exploratory biomarker, and pharmacogenomic variables are listed in Section 4.2 and immunogenicity variables are listed in Section 4.3.

Safety variables to be assessed are adverse events (AEs), vital signs, physical examination, and measurements of laboratory parameters. In addition, subjects will be evaluated at Screening, Baseline, and at every 12 weeks thereafter up to Week 36 and including Week 52/Withdrawal (WD) (for subjects not participating in the SFE Period) for signs and symptoms of latent or active tuberculosis (TB) infection and risk factors for exposure to TB using the TB questionnaire.

Approximately 1200 subjects will be screened in order to have 300 subjects (150 subjects per treatment group) randomized into the study. Randomization will be stratified by presence of sacroiliitis on MRI and elevated CRP to ensure balanced treatment allocation across 3 subgroups: MRI+/CRP+; MRI+/CRP-; MRI-/CRP+.

For each subject, the study will consist of 3 periods and will last a maximum of 66 weeks:

- Screening Period lasting up to 6 weeks
- Double-Blind, Placebo-Controlled Period for 52 weeks
- FU Period 8 weeks after the Week 52/WD visit (for subjects not participating in the SFE Period).

For subjects participating in the SFE Period, the study will extend up to a maximum of 104 additional weeks.

The estimated recruitment period is up to 15 months. The first subject first visit is planned in Quarter 3 2015. The end of the study will be defined as the date of the last subject's last visit, defined as the FU visit 8 weeks after the Week 52/WD visit for subjects not participating in the SFE Period, or the last visit of the SFE Period.

---

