#### **8.5 Week 52/WD ( $\pm$ 3 days)**

A subject is regarded to have completed the Double-Blind Period of the study if s/he completes the Week 52 assessments. Assessments at this visit include:

- Vital signs; pulse rate, systolic and diastolic blood pressure, and temperature (respiration rate will be assessed in addition if the subject experiences an AE)
- Blood samples (subjects should be encouraged to be under fasting conditions, the same condition [fasting or not fasting] should be applied at Week 52) will be collected for hematology, biochemistry, and CRP (biochemistry assessment will include the measurement of Apo A1, ApoB, lipoprotein(a), and HbA1c)
- Urine will be collected for urinalysis and for a urine pregnancy test for women of childbearing potential
- Physical examination (including weight)
- Extra-articular assessments
- Chest x-ray only if the TB test was confirmed positive or any further evidence is suggestive of potential TB infection
- TB test: IGRA test (QuantiFERON test [or Elispot test when QuantiFERON test is indicated but not available]) only for subjects who have not had a previously positive TB test result
- TB Questionnaire
- SI joint x-ray
- MRI for spine and SI joints (at Week 52/WD visit if previous MRI was performed more than 12 weeks prior to Week 52/WD visit)
- BASMI and spinal mobility
- BASDAI
- BASFI
- SF-36
- ASQoL
- EQ-5D
- MASES
- Total spinal pain NRS and nocturnal spinal pain NRS

- 
- Swollen and tender joint counts
  - PhGADA
  - PGADA
  - Productivity measures (WPS)
  - Resources utilization
  - Plasma for CZP concentration, anti-CZP antibodies, and biomarkers
  - Gene expression and proteomics, if applicable
  - Concomitant medication
  - AEs
  - Contact IXRS to indicate that subject has rolled over to the SFE Period or withdrawn from the study

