### **8.9 Alternative visit schedules after subject discontinuation of the double-blind study treatment**

Subjects who discontinue the double-blind study treatment and enter open-label treatment with CZP will be assessed 2 and 4 weeks after open-label CZP treatment has been initiated and every 12 weeks thereafter. Alternatively, subjects who discontinue the double-blind study treatment and receive other treatment (including biologics) will be assessed every 12 weeks after initiation of the other treatment. The alternative schedules for open-label CZP and other treatment can be found in [Table 5-2](#) and [Table 5-3](#), respectively. In either alternative schedule, assessments should be conducted until as close as possible to Week 52 (within  $\pm 4$  weeks), where Week 52 is relative to the original randomization at Week 0. Subjects will then be invited to the final assessment visit at Week 52.

The following assessments will be performed for subjects who are treated with open-label CZP after discontinuation of the double-blind study treatment:

- Vital signs; pulse rate, systolic and diastolic blood pressure, and temperature (respiration rate will be assessed in addition if the subject experiences an AE) at wdt Weeks 0, 2, 4, 12, 24 (and every 12 weeks [Q12W]), 52, and FU (8 weeks after Week 52 Visit)
- Blood samples will be collected for hematology, biochemistry, and CRP analyses, and urine will be collected for urinalysis at wdt Weeks 0, 12, 24 (and Q12W), 52 and FU (8 weeks after Week 52 Visit)

Note: Fasting blood samples will be collected for hematology, biochemistry, and CRP analyses at wdt Week 0 (biochemistry assessment will include the measurement of Apo A1, ApoB, lipoprotein(a), and HbA1c). At Week 52, the biochemistry assessment will include the measurement of HbA1c.

- Pregnancy test for women of childbearing potential at wdt Weeks 0, 52 (urine testing), and FU (serum testing)
- Physical examination at wdt Weeks 0, 4, 12, 24 (and Q12W), 52, and FU
- Extra-articular assessments at wdt Weeks 12, 24 (and Q12W), and 52
- TB test at wdt Week 52 only
- TB questionnaire at wdt Weeks 0, 12, 24 (and Q12W), and 52
- SF-36, AsQoL, MOS Sleep Scale, EQ-5D, and MASES at wdt Weeks 0, 12, 24 (and Q12W), and 52
- BASMI & spinal mobility, BASFI, total and nocturnal spinal pain, swollen and tender joint counts, BASDI, Patient's Global assessment, and Investigator's AS assessment at wdt Weeks 0, 4, 12, 24 (and Q12W), and 52

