## 12 ASSESSMENT OF SAFETY

Safety variables to be assessed are physical examinations, AEs, vital signs, and measurements of laboratory parameters.

Adverse events will be solicited at every visit, and recorded and coded according to the latest version of the Medical Dictionary for Regulatory Activities (MedDRA®) criteria.

Physical examination findings will be recorded in the CRF only at Screening. Clinically important abnormal changes in subsequent physical examinations will be recorded as AEs at all visits from Baseline to the FU visit.

Clinical laboratory values (hematology, biochemistry, urinalysis) will be collected and assessed at Screening, Baseline, Weeks 2, 4, 8, 12, 24, 36, at the end of study completion at Week 52/WD visit and at the FU visit (8 weeks after the Week 52/WD visit). In addition, clinical laboratory values will be collected and assessed at study visits during the administration of open-label CZP in subjects who withdraw from the double-blind study treatment.

Furthermore, CRP will be collected and assessed either in a blinded or open manner at Screening, 3 to 5 days before Baseline, Weeks 2, 4, 8, 12, 16, 20, 24, 28, 32, 36, 40, 44, 48, and at the end of study completion at Week 52/WD visit and at the FU visit (8 weeks after the Week 52/WD visit).

At Screening, all subjects will have an IGRA test (QuantiFERON® TB test or Elispot® test, when the QuantiFERON test indicated is not available), and a chest x-ray reading (or, if done, computed tomography of the chest) which must be reported consistent with standard clinical reporting practice by an experienced qualified TB specialist, radiologist, or a pulmonologist, who is specifically required to look for signs of active TB or signs of past/inactive TB infection. A chest x-ray will not be done at Screening if a chest x-ray (or computed tomography of the chest) was done within 3 months prior to the Screening visit. The official report of the imaging must specifically indicate the absence of findings suggestive of current active TB or prior inactive TB. In addition to a physical examination done intermittently throughout the study, subjects will be evaluated at Screening, Baseline, and every 12 weeks thereafter up to Week 36 and including the Week 52/WD visit, for signs and symptoms of LTB or active TB infection and risk factors for exposure to TB using the TB questionnaire.

---

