### 12.6.3.1 Tuberculosis assessments

During conduct of the study the TB assessment by IGRA will be performed at Screening and should be repeated at Week 52/WD for all subjects not participating in the SFE Period. It is recommended that TB testing be performed according to local standard medical practice during the SFE Period.

The test results will be reported as positive, negative, or indeterminate and must be reviewed by an experienced TB specialist, radiologist, or a pulmonologist. If the assessment by IGRA is positive or indeterminate on retest for subjects who were previously negative at Screening and not treated for LTb, the subject may not continue study treatment without further evaluation by a TB specialist, prophylactic TB treatment, and discussion with the Medical Monitor, if LTb infection is identified. If active TB is identified, subject must undergo appropriate study specified withdrawal procedures. The retest must be done during the protocol-defined Screening window.

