### 12.6.3.3 QuantiFERON or Elispot testing

At Screening all subjects will have an IGRA test (QuantiFERON tube test or Elispot, if QuantiFERON test indicated is not available). The TB test will be repeated at completion at Week 52/WD for subjects not participating in the SFE Period. It is recommended that TB testing be performed according to local standard medical practice during the SFE Period. Results of the tests will be reported as positive, negative, or indeterminate.

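### The Protocol conflicts on whether SFE entrants have the mandatory Week 52 IGRA, and on whether latent TB is reported as an SAE or as an AESI

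*Protocol*

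**What the plan says.** **Week 52 IGRA.**
- Section 12.6.3.1: the IGRA is done at Screening and "should be repeated at Week 52/WD for all subjects not participating in the SFE Period". Section 12.6.3.3 agrees: "The TB test will be repeated at completion at Week 52/WD for subjects not participating in the SFE Period". In both sections the next sentence recommends TB testing by local standard practice during the SFE.
- Section 8.5 lists the Week 52/WD IGRA "only for subjects who have not had a previously positive TB test result". That is its only restriction; SFE participation is not mentioned.
- Section 8.9, for subjects switched to open-label CZP, lists "TB test at wdt Week 52 only", again without an SFE exemption. These subjects are eligible for the SFE.
- Sections 6.4 and 8.6 require SFE entrants to have completed the Week 52 assessments. Table 5-6, footnote a, refers them to Tables 5-1 and 5-2 for those assessments.

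**Week 52 TB questionnaire.** The Summary carries the same exemption: "including Week 52/Withdrawal (WD) (for subjects not participating in the SFE Period) for signs and symptoms of latent or active tuberculosis". Section 8.5 lists the questionnaire without it, as does Section 8.9: "TB questionnaire at wdt Weeks 0, 12, 24 (and Q12W), and 52". Section 12 has it "every 12 weeks thereafter up to Week 36 and including the Week 52/WD visit", and Section 12.6.3.4 agrees.

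**Chest x-ray.** Section 12.6.3.2 repeats the x-ray at Week 52/WD after a positive TB test only for subjects outside the SFE; inside the SFE it is only recommended. Section 8.5 makes no such distinction.

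**Latent TB.** Section 12.6.3, under Latent TB, requires latent TB to be reported as an SAE. Section 12.6.3.5 has confirmed active TB reported as an SAE and confirmed latent TB as an AESI, citing Sections 12.2 and 12.3. Section 12.2.1 names only confirmed active TB, and the Section 12.3 list does not name latent TB.

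**The concern.** A site cannot both apply the exemption in Sections 12.6.3.1 and 12.6.3.3 and meet the entry condition in Sections 6.4 and 8.6, if that condition is read with the assessments listed in Sections 8.5 and 8.9. The subjects affected are those about to start or continue a TNF inhibitor, and Section 12.6.3 itself notes the risk of latent TB reactivation with that class. The sharpest case is the placebo completer, who under Section 7.2.1 receives CZP 400 mg at Weeks 52, 54 and 56.

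The latent TB conflict is a reporting matter. Section 4.4.1 makes SAE incidence a secondary safety variable. If sites follow different sentences, the same event is counted as serious at one site and not at another.

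**Working it through.** The check is mainly a comparison of current text. The amendment history was not used. The TB rows of Table 5-1 could not be read in the available copy, so nothing here rests on them.

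| Item | Exempts SFE entrants | No exemption |
|---|---|---|
| Week 52 IGRA | 12.6.3.1, 12.6.3.3 | 8.5, 8.9; entry condition in 6.4, 8.6 |
| Week 52 questionnaire | Summary only | 8.5, 8.9, 12, 12.6.3.4 |
| X-ray after a positive test | 12.6.3.2 | 8.5 |

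| Latent TB class | Section |
|---|---|
| SAE | 12.6.3 (Latent TB) |
| AESI, set against active TB as SAE | 12.6.3.5 |
| Not named | 12.2.1, 12.3 |

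**Age of the last required IGRA if the exemption is applied.** Inputs: Screening starts up to 6 weeks before Baseline (Sections 5.1.2 and 8.1); the first SFE dose is at Week 52 (Section 7.2.1).
- 6 + 52 = 58 weeks at most. The permitted roll-over delay of up to 3 months (Sections 5.1.1 and 6.4) is not added and could only lengthen this.

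**Age of the last questionnaire if the Summary were followed.** For double-blind completers the last one before Week 52 is at Week 36 (Section 8.3): 52 − 36 = 16 weeks. This does not apply to open-label CZP subjects, who complete it every 12 weeks (Section 8.9).

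**Can the remaining check substitute?** Section 12.6.2 keeps the TB signs-and-symptoms assessment at Week 52. Section 12.6.3 says, however, that a subject may have a positive IGRA with no signs, symptoms or physical findings. A clinical check therefore cannot be relied on to find latent infection.

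**Effect of the latent TB rule on SAE incidence.** Input: 150 subjects planned per arm (Section 14.10). For one confirmed latent TB event that meets no other seriousness criterion, in a subject with no other SAE:
- under Section 12.6.3: 1/150 = 0.0067, or 0.67 percentage points;
- under Section 12.6.3.5: 0.

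The Protocol gives neither a latent TB rate nor an SFE roll-over rate, so no count of events or of affected subjects can be derived.

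**The case against.** The exemption looks deliberate. Sections 12.5 to 12.6.4 move most SFE monitoring to local practice: laboratory tests, pregnancy tests, physical examination, x-ray and vital signs. On a specific-over-general reading, the Week 52 assessments required for SFE entry are those that apply to the subject, and the defect is only a missing cross-reference in Sections 8.5 and 8.9. This carries weight as to intent. It does not remove the conflict, because Sections 6.4, 8.5, 8.6 and 8.9 were left without the exemption and a site cannot tell which text governs.

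A reader might infer that SFE entrants go untested for TB. The text does not support that: local testing is recommended during the SFE. What is lost is a mandatory test with a fixed time before the first SFE dose.

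A reader might also infer that Section 12.6.3.1 contradicts itself, since its second paragraph says of a newly positive subject that "the subject may not continue study treatment without further evaluation by a TB specialist, prophylactic TB treatment, and discussion with the Medical Monitor", while the scheduled repeat goes only to subjects with no further study drug. That is not established. The paragraph also carries Screening-retest wording, and its stop rule can apply to results obtained locally during the SFE.

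The questionnaire conflict is minor. It sits in a parenthesis in the Summary against four operative sections, and a site is unlikely to drop the questionnaire on that basis.

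On latent TB, an event can be both an SAE and an AESI; Section 12.6.3 says so for active TB. Section 12.6.3.5, however, contrasts the classes and gives latent TB only the AESI label. Section 12.4 requires immediate reporting of both SAEs and AEs of interest, so lost or delayed reports should not be inferred. Equally, with latent TB absent from Section 12.3, immediate reporting under the AESI route is not fully secured. Blinded classification gives no reason to expect bias between arms, and SAE incidence is not in the testing hierarchy of Section 14.2.

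**Conclusion.** The concern holds in this form: the Protocol conflicts on the mandatory Week 52 IGRA for SFE entrants and on the reporting class of latent TB, with a minor matching conflict on the questionnaire. A site following the exemption could start a placebo completer on CZP loading with a required IGRA up to 58 weeks old. This assumes Screening at the earliest permitted time, the first SFE dose at Week 52, and no local test in between. The latent TB rule moves an arm's SAE incidence by 0.67 percentage points per otherwise non-serious event, at the planned arm size and for a subject with no other SAE. No event count is claimed, and sample size, alpha, power and the efficacy analyses are untouched. This is a safety-conduct and reporting matter that should be fixed.

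**What to change.** **1. Week 52 testing.** Delete the SFE exemption in the Summary and in Sections 12.6.3.1 and 12.6.3.3, and keep the local-practice recommendation for testing after Week 52. Have the Week 52 IGRA result reviewed before the first SFE dose where feasible; the 3-month roll-over allowance leaves room for this. Otherwise handle a positive result under Section 12.6.3. Align Section 12.6.3.2 so that a positive Week 52 test leads to a chest x-ray in SFE entrants too.

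**2. Latent TB.** State one rule in Section 12.6.3 (Latent TB) and Section 12.6.3.5, and add latent TB to Section 12.3. Confirmed latent TB is reported immediately as an AE of interest, and also as an SAE if it meets a Section 12.2.1 criterion, including the investigator's judgment that it is an important medical event. Apply the rule prospectively. Query inconsistent earlier reports before database lock, without downgrading any event the investigator judged serious.

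**Cost.** Wording in the Summary and Sections 12.3, 12.6.3, 12.6.3.1, 12.6.3.2, 12.6.3.3 and 12.6.3.5, a note to sites, and a query round on latent TB reports. Measured against Sections 8.5 and 8.9, no test is added. For sites that have been applying the exemption, the change means one more IGRA per SFE entrant without a previous positive test, and possibly a short wait for its result.

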#### 5.1.1 Study periods

The study includes 3 periods. An injection schedule is provided in [Section 7.2.2](#).

**Period 1** (Screening Period): 1 day to 6 weeks before Baseline:

Prior to any study activities, subjects will be asked to read and sign the Informed Consent form for the conduct of the study. A separate informed consent form will also be obtained from subjects consenting to the use of their blood samples in a substudy for possible genetic/epigenetic, genomic, proteomic, and metabolite analysis.

Laboratory data (hematology, urine, and biochemistry tests) will be obtained, and treatment of latent tuberculosis (LTB) will be initiated when necessary. Subjects must undergo a TB test and complete a TB questionnaire. The BASDAI, BASMI, and spinal mobility assessments will be performed. Concomitant medications permitted during the study should remain stable for at least 4 weeks prior to Baseline at Week 0.

Sacroiliac-joint x-ray (not older than 12 months before Baseline and verified by central reading during the Screening Period) must prove that the subject belongs to the mNY-negative axSpA

subpopulation, ie, does not have sacroiliitis grade  $\geq 2$  bilaterally or grade 3 to 4 unilaterally. Potentially eligible axSpA subjects without suitable SI-joint x-ray must undergo the x-ray with central reading within the Screening Period. Sacroiliac-joint x-rays (read centrally) will allow discrimination of subjects with AS and without definitive evidence for sacroiliitis on x-ray (mNY negative-axSpA). Subjects with AS (mNY-positive) must be excluded from further participation in this study.

Confirmed mNY-negative axSpA subjects must undergo an MRI later during the Screening Period for central reading with results from the central reading available by no later than at the Baseline visit.

Additionally, the subjects must get a further measurement of CRP 3 to 5 days before Baseline (Week 0).

**Period 2 (Double-Blind Period):** Week 0 to Week 52, placebo-controlled.

Eligible subjects will be allocated to the following double-blind study treatments in a 1:1 ratio:

- CZP administered at the dose of 400mg at Weeks 0, 2, and 4 followed by 200mg Q2W (starting at Week 6 up to and including Week 50)
- Placebo

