### 6.3 Withdrawal criteria

Subjects are free to withdraw from the study at any time, without prejudice to their continued care.

Subjects should be withdrawn from the study if any of the following events occur:

1. Subject develops an illness that would interfere with his/her continued participation.
2. Subject is noncompliant with the study procedures or medications in the opinion of the Investigator.
3. Subject withdraws his/her consent.
4. There is confirmation of a pregnancy during the study, as evidenced by a positive pregnancy test (see [Section 12.1.6](#) for more information regarding pregnancies).
5. The Sponsor or a regulatory agency requests withdrawal of the subject.
6. Subject's subsequent TB test was confirmed positive or any further evidence is suggestive of potential TB infection (eg, exposure). Refer to [Section 12.6.3](#) for further details and instructions.

Subjects should be withdrawn from the study-treatment if,

7. The Investigator decides to initiate an alternative treatment due to an unsatisfactory response to the study treatment, or
8. Subjects take any of the prohibited medications in [Table 7–1](#) and [Section 7.8.2](#)

If a subject is withdrawn from the double-blind study treatment, the Investigator should encourage the subject to continue participation in the study in accordance with the appropriate alternative schedule of study assessments ([Table 5–2](#) or [Table 5–3](#)). The treatment that the subject receives following withdrawal of study medication is at the discretion of the Investigator,

with open-label CZP available as a treatment option according to the local requirement mandated in the region. UCB will provide this medication free of charge. Alternatively, the Investigator may treat the subject with other treatments (including biologics) as deemed appropriate by local regulations. If the Investigator chooses to withdraw subjects on the other therapy, the local guidelines on initiation and monitoring of the particular treatment should be followed.

Investigators should contact the Medical Monitor, whenever possible, to discuss the withdrawal of a subject from the double-blind study treatment in advance. The reason for discontinuation of the double-blind study treatment must be recorded in the case report form (CRF) as appropriate.

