  - Urine will be collected for urinalysis (Weeks 2, 4, 8, 12, 24, and 36 only)
  - Physical examination (Weeks 2, 4, 8, 12, 16, 24, and 36), including weight at Week 24
  - Extra-articular assessments (Weeks 4, 12, 24, 36, and 48 only)
  - TB questionnaire (Weeks 12, 24, and 36 only)
  - MRI (spine and SI joints; Week 12 only)
  - BASMI and spinal mobility (at all on-site visits except Weeks 6, 10, and 50)
  - BASDAI (Weeks 1, 2, 4, 8, 12, 16, 20, 24, 28, 32, 36, 40, 44, and 48 only)
  - BASFI (Weeks 1, 2, 4, 8, 12, 16, 20, 24, 28, 32, 36, 40, 44, and 48 only)
  - SF-36 (Weeks 4, 12, 24, 36, and 48 only)
  - ASQoL (Weeks 1, 2, 4, 12, 24, 36, and 48 only)
  - MOS Sleep Scale (Weeks 4, 12, 24, 36, and 48 only)
  - EQ-5D (Weeks 4, 12, 24, 36, and 48 only)
  - MASES (Weeks 1, 2, 4, 8, 12, 16, 24, 32, 40, and 48 only)
  - Total spinal pain NRS and nocturnal spinal pain NRS (Weeks 1, 2, 4, 8, 12, 16, 20, 24, 28, 32, 36, 40, 44, and 48 only)
  - Swollen and tender joint counts (Weeks 4, 12, 24, and 36 only)
  - PhGADA (Weeks 1, 2, 4, 8, 12, 16, 20, 24, 28, 32, 36, 40, 44, and 48 only)
  - PGADA (Weeks 1, 2, 4, 8, 12, 16, 20, 24, 28, 32, 36, 40, 44, and 48 only)
  - Productivity measures (WPS) (Weeks 4, 12, 24, 36, and 48 only)
  - Resource utilization (Weeks 4, 12, 24, 36, and 48 only)
  - Plasma for CZP concentration, anti-CZP antibodies, and biomarkers (Weeks 1, 2, 4, 12, 24, and 36 only)
  - Genetics and epigenetics (Week 12 only), if applicable
  - Gene expression and proteomics (Weeks 4 and 12), if applicable
  - Concomitant medication
  - AEs
  - Contact IXRS to register the visit and obtain next kit number, where applicable (Weeks 2, 4, 6, 8, 10, 12, 16, 20, 24, 28, 32, 36, 40, 44, 48, and 50)
  - Study drug administration (after all other visit assessments are completed and laboratory samples are drawn) (all visits except Week 1)
  - Subject training on self-injection (Weeks 10 and 12)

---

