#### Signs and Symptoms

The Investigator should consider all potential sites of infection when assessing for TB during the subject's history and the physical examination, and other evaluations. Sites commonly infected by TB include: the lungs, larynx, lymph glands, pleura, gastrointestinal system, genito-urinary tract (including renal), bones and joints, meninges, peritoneum, pericardium, and skin. This is not an exhaustive list and unusual presentations and areas of involvement should always be considered.

Common symptoms that the subject may present with include cough, blood in sputum, night sweats, lymphadenitis, joint pain/swelling, spinal deformity, headache/confusion, abdominal pain mimicking IBD, frequent or painful urination, scrotal mass in men and pelvic inflammatory disease in women as well as other symptoms, or nonspecific symptoms. This is not an exhaustive list and unusual presentations should always be considered.

The subject may present an absence of signs, symptoms (ie, evidence of organ-specific involvement), or physical findings suggestive of TB infection with a positive IGRA test (or 2 indeterminate IGRA test results) and a chest x-ray (or other imaging) without evidence of TB infection. If the result of the IGRA test is indeterminate, the particular IGRA test previously performed may be repeated once; if positive or indeterminate on retest, the subject may not be randomized to study medication without further evaluation, treatment, and discussion with Study Physician, if LTB infection is identified. (If active TB is identified, subject must undergo

---

appropriate study-specified withdrawal procedures.) The retest must be done during the protocol-defined Screening window.

Note: If available, respiratory or other specimens must also be smear and culture negative for TB (CDC diagnosis of LTB infection [<http://www.cdc.gov/TB/topic/testing/default.htm>]).

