#### Test Conversion

Tuberculosis test conversion is defined as a positive result (IGRA) for the current test but previous test results were negative (IGRA). All subjects with TB test conversion must immediately stop study drug administration. In case of a TB test conversion, the subject must be considered as having either a suspected new LTB or an active TB infection and be promptly referred to an appropriate specialist (ie, pulmonologist, infectious disease specialist) must be consulted for further evaluation. If test conversion indicates LTB infection, active TB, or nonmycobacterial TB infection then per UCB TB working instructions, TB test conversion (confirmed) should be classified as due to LTB infection, active TB infection, or NTMB infection. Additional assessments (eg, blood tests or IGRA test, chest x-rays or other imaging) should be performed as medically indicated.

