#### **LTB infection and active TB identified during study**

During the study, subjects who develop evidence of LTB infection or active TB must immediately stop further administration of study medication and will be referred to an appropriate TB specialist (pulmonologist or infectious disease specialist) for further evaluation. Evidence of LTB infection is defined as subject’s IGRA test converts to positive or indeterminate (and confirmed indeterminate on repeat), or the subject’s questionnaire or history and physical indicates that TB infection or exposure may have occurred. Evidence of active TB includes, in addition to the aforementioned tests, signs and symptoms of organ involvement. In either situation, the subject should be carefully assessed by a TB specialist for active TB. Subjects diagnosed with active TB or LTB infection should receive appropriate TB or prophylaxis therapy.

If a TB specialist excludes an active TB infection the subject can proceed with the study drug no earlier than 4 weeks after the start of an appropriate prophylactic therapy.

Any presumptive diagnosis or diagnosis of a TB infection is a reportable event. Confirmed active TB must be reported as an SAE; confirmed LTB as AESI (please see Sections 12.2 and 12.3). The Investigator is to complete and submit the TB follow up form provided.

The subject should be transferred to the care of his/her physician and managed according to the best available standard of care. Subjects identified as having converted to active TB during the study must be withdrawn and scheduled to return for the Week 52/WD visit as soon as possible but no later than the next scheduled study visit and complete all Week 52/WD visit assessments.

The subject should be encouraged to complete a FU visit (8 weeks after the Week 52/WD visit).

If infection with NTMB is identified during the study, the same procedure as for active TB acquired during the study must be followed.

Subjects with LTB infection must not undergo IGRA testing. The IGRA test should be used for any protocol mandated monitoring.

Follow-up information of suspected and confirmed TB cases should be provided to UCB at least after 3, 9, and 12 months of the start date of anti-TB treatment, including hematological and biochemical safety parameters, x-ray evolution data, and TB diagnostic procedures used to follow up and confirm recovery of TB.

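### Section 12.6.3.1 puts the retest for an on-treatment TB rule inside the Screening window, which has already closed, so an indeterminate on-study IGRA cannot be repeated as written

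*Protocol*

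**What the plan says.** Section 12.6.3.1 (Tuberculosis assessments) schedules the IGRA at Screening and again at Week 52/WD for subjects not entering the SFE Period. It then sets a rule for a later result that is either positive or still indeterminate when repeated. The rule reads: "for subjects who were previously negative at Screening and not treated for LTb, the subject may not continue study treatment without further evaluation". A TB specialist makes that evaluation, and if latent infection is found, prophylaxis and discussion with the Medical Monitor are also required. If active TB is found, withdrawal procedures apply. The paragraph closes with "The retest must be done during the protocol-defined Screening window".

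Section 5.1.1 defines the window for Period 1: "Screening Period): 1 day to 6 weeks before Baseline".

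Section 12.6.3 (Signs and Symptoms) has the identical closing sentence after a different rule. There, an indeterminate IGRA may be repeated once, and "if positive or indeterminate on retest, the subject may not be randomized to study medication without further evaluation".

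Section 12.6.3.5, on infection identified during the study, counts as evidence of latent TB that the subject's "IGRA test converts to positive or indeterminate (and confirmed indeterminate on repeat"), or that the questionnaire, history or physical examination points to infection or exposure.

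**The concern.** The rule in Section 12.6.3.1 can apply only after dosing has begun, yet it ties its retest to a period that ended before dosing. A site that obtains an indeterminate IGRA on study treatment reads in Section 12.6.3.5 that a repeat is expected, and in Section 12.6.3.1 that the repeat belongs in a window already closed.

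Taken literally, the repeat cannot be done in compliance, and the indeterminate route to evidence of latent TB in Section 12.6.3.5 can never be completed. The site must then repeat the test against the text, act on a single unconfirmed result, or leave the result unconfirmed. The subject may be receiving a TNF inhibitor, a class that Section 12.6.3 links to reactivation of latent TB. What is at stake is the clarity of a safety rule, not any efficacy result.

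**Working it through.** No statistical calculation applies, and the plan gives no figure to reproduce. The check compares timing and wording.

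1. **When the window closes.** Section 5.1.1 runs Screening from 6 weeks to 1 day before Baseline, so its last day is Day -1.

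2. **When the 12.6.3.1 rule can apply.** Two features place it after Baseline. The subject was already negative at Screening, and the consequence concerns continuing treatment, which starts at Week 0. The scheduled later IGRA is at Week 52/WD. A Week 52 test therefore comes about 52 weeks after the window closed. An earlier unscheduled or withdrawal test still comes after first dose, hence after Day -1.

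3. **Whether parsing rescues the sentence.** The retest could be the repeat of an indeterminate on-study result, or it could be the later IGRA itself seen as a retest of the Screening one. Both fall after Screening, so the sentence cannot be met under either reading.

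4. **Where the sentence fits.** The two rules side by side:

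| | Section 12.6.3 | Section 12.6.3.1 |
|---|---|---|
| Subject | Not yet randomized | Negative at Screening, on study treatment |
| Decision | Whether to randomize | Whether to continue treatment |
| Retest in Screening window | Possible | Impossible |

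The parallel wording suggests that the sentence was carried over from Section 12.6.3, but the amendment log does not document this.

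5. **Whether the sentence is current.** It stands in the body of the protocol. Protocol Amendment 3 (Change #37) revised only the opening of Section 12.6.3.1 and left this sentence in force.

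6. **Which on-study results depend on a retest.**
 - Positive: Section 12.6.3 (Test Conversion) defines conversion as a positive result after earlier negative ones and requires study drug to stop at once. No retest is needed.
 - Questionnaire, history or physical examination suggesting infection or exposure: Section 12.6.3.5 already counts this as evidence and stops study medication. No retest is needed.
 - Indeterminate: this is outside the definition of conversion. It becomes evidence of latent TB under Section 12.6.3.5 only when confirmed on repeat. This is the one route that needs an on-study retest, and Section 12.6.3.1 makes that retest impossible.

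**The case against.** The best defence is that the sentence refers only to repeating an indeterminate Screening IGRA, since the paragraph also mentions the Screening test. This reading is weak. The only retest named in Section 12.6.3.1 concerns subjects already negative at Screening, and Section 12.6.3 already covers the Screening repeat in the same words.

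A second defence is that nothing follows in practice: results must be reviewed by a specialist, conversions stop drug at once, actions on latent TB are discussed with the Medical Monitor, and Section 8.8 permits TB testing at unscheduled visits. Much of this stands and is why the severity is low. It does not remove the contradiction for an indeterminate result.

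Four stronger readings are tempting, and the documents do not support them.

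- **The sentence also contradicts withdrawal criterion 6 and the Test Conversion text.** Criterion 6 in Section 6.3 refers to a case where the "subsequent TB test was confirmed positive or any further evidence is suggestive of potential TB infection", but it does not say that confirmation means a repeat IGRA. The Test Conversion text says "Additional assessments (eg, blood tests or IGRA test, chest x-rays or other imaging) should be performed as medically indicated", which is optional work-up after a positive result. Only Section 12.6.3.5 clearly presupposes an on-study repeat.
- **The sentence bites whenever a TB questionnaire raises a concern.** A questionnaire indicating possible infection or exposure already stops drug under Section 12.6.3.5. Counting questionnaire visits would not count retests.
- **Subjects with possible TB would stay on drug.** The stopping rules above do not depend on the faulty sentence.
- **The Week 52 test in subjects entering the SFE Period is part of this problem.** Whether those subjects need a Week 52 IGRA is a separate inconsistency and does not arise from this sentence.

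**Conclusion.** The sentence is wrong where it stands in Section 12.6.3.1, and the error is of low severity. It conflicts with one other current provision, the repeat expected in Section 12.6.3.5, and its practical reach is limited to indeterminate on-study IGRA results. The protocol gives no frequency for such results, so the number of subjects affected cannot be stated.

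The conclusion rests on reading Section 12.6.3.1 as an on-treatment rule, which its reference to subjects negative at Screening and to continuing study treatment makes hard to avoid. Efficacy endpoints, sample size, power and type I error are unaffected.

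**What to change.** Delete the Screening-window sentence from Section 12.6.3.1 and keep it in Section 12.6.3, where it governs randomization. An indeterminate on-study IGRA is then repeated on study and handled under Section 12.6.3.5, at an unscheduled visit under Section 8.8 where needed. Adding that the repeat is done promptly would help sites but is optional.

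The cost is one deleted sentence in the next amendment. No Screening requirement is lost, no test is added beyond the repeat that Section 12.6.3.5 already expects, and no analysis changes.
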